## 29.0 Data and Specimen Management\*

### 29.1 Data Management: *Describe how data will be handled, including:*

- *How the data will be collected and stored. (e.g., REDCap, Excel, paper forms)*
- *How long the data will be stored.*
- *Who will have access to the data.*
- *Who is responsible for receipt or transmission of the data.*
- *Methods for transferring data.*

Data will be stored in redcap until study concludes with monthly data reports delivered via secure email to those included in the DUA. Data from Willow will be provided by serial number for data matching to Redcap data. Redcap is designated for research purposes at the academic medical center. Data will be quantitatively analyzed via SAS by the biostatistical partner, contracted through the institution. Willow will provide

Individual users will be deidentified data and enrolled in the study by serial number for data matching with Willow application data.

Investigators will have access to the data for analysis and aggregate reporting purposes. Data stored on secure internal network drives. Investigators are responsible for receipt and any transfer of the data through secure network tools.

### 29.2 Specimen Management: *Describe how specimens will be handled, including:*

N/A

**29.3 Biosafety Information**

1. Will this study involve handling, transporting, or shipping any potentially hazardous biological material at/from a Children's Mercy location (e.g., blood, stool, saliva, tissue)?

Yes

No

2. Will this study involve processing any potentially hazardous biological material at a Children's Mercy location (e.g., blood, stool, saliva, tissue)?

Yes

No

3. If processing potentially hazardous biological materials, where will this work be conducted?

Pediatric Clinical Research Unit (PCRU)

Children's Mercy Research Institute Biorepository (CRIB)

Children's Mercy Research Institute labs (mySafety ID#: \_\_\_\_\_)

Other location

If "Other location," identify the location and mySafety ID# of the corresponding IBC protocol:

Location: \_\_\_\_\_

mySafety ID#: \_\_\_\_\_

4. List the material(s)/agent(s) that will be processed at Children's Mercy: (List)

- 

## 30.0 Storing of Data and/or Banking of Specimens for Future Research

**30.1** *If this study involves storing of data or banking of leftover specimens for future research, indicate how the use will be managed:*

- Contributing data and/or leftover specimens to an existing CM repository protocol (myIRB# \_\_\_\_\_)
- Contributing data and/or leftover specimens to an existing non-CM repository (Institution/Repository Name: \_\_\_\_\_)
- Not contributing to an existing repository for the management of data/specimens for future research use.
- Other:

**30.2** *If not contributing to an existing repository, describe:*

- *What data/specimens will be stored.*
- *Where the data/specimens will be stored.*
- *How long they will be stored.*
- *How the data/specimens will be accessed.*
- *Who will have access to the data/specimens.*
- *Describe the procedures to release data or specimens, including: the process to request a release, approvals required for release, who can obtain data or specimens (e.g. CM research only, external researchers), and the data/identifiers to be provided with specimens.*
- *If study population includes minors whose specimens will be retained for long term research, be sure to address plans for when participants turn 18 years of age. The process may include re-contacting and obtaining consent, de-identifying samples when participants turn 18, or requesting to waive the requirement of consent at 18.*

Data will be stored in redcap until study concludes with monthly data reports delivered via secure email to those included in the DUA. Data from Willow will be provided by serial number for data matching to Redcap data. Redcap is designated for research purposes at the academic medical center. Data will be quantitatively analyzed via SAS by the biostatistical partner, contracted through the institution.

## 31.0 Provisions to Monitor the Data to Ensure the Safety of Participants

*This section is required when research involves more than Minimal Risk to participants.*

**N/A**

**31.1** *In addition to the Principal Investigator, which individual or group will be responsible for monitoring the data and safety for this study?*

- Sponsor or Sponsor Designee (including the Sponsor CRO)
- Data and Safety Monitoring Board (DSMB) or Data Safety Monitoring Committee (DSMC)
- Independent Monitor (s)
- Internal Committee at CM
- Other: \_\_\_\_\_

**31.2 Data Safety Monitoring Plan:** *If a DSMB charter or other external monitoring plan is available, upload in the myIRB application, Other Attachments section. If such a charter/plan is not available, describe:*

- *The plan to periodically evaluate the data collected regarding both harms and benefits to determine whether participants remain safe. The plan might include establishing a data monitoring committee and reporting data monitoring committee findings to the IRB and the sponsor. For NIH funded research, see requirements for [Data and Safety Monitoring](#)*
- *What data are reviewed, including safety data, untoward events, and efficacy data.*
- *How the safety information will be collected (e.g. with case report forms, at study visits, by telephone calls with participants).*
- *The frequency of data collection, including when safety data collection starts.*
- *Who will review the data.*
- *The frequency or periodicity of review of cumulative data.*
- *The statistical tests for analyzing the safety data to determine whether harm is occurring.*
- *Any conditions that trigger an immediate suspension of the research.*

*Participation is fully voluntary and there will be no undue influence to pump if a participant is unhappy or unable to use the devices, individuals will need to let us know when they are done so Investigators can send them the final survey and remove them from the monthly send. Our survey will ask questions about what made them*

*stop pumping and there is an open text box for those that would like to provide any detail about their experience.*

Individuals will be surveyed monthly on basic data but will be asked to assess if they are satisfied with the device, and utilization, Investigators will ask users to let us know when they cease pumping so Investigators can send the outtake survey (probably link it to the monthly survey) and then Investigators will end monthly survey Data reviewed monthly will include number of active users in the study, volume of milk and frequency of pumping. Quarterly review of satisfaction with Willow devices and utilization of other resources will be reviewed in aggregate. Early cessation in the study will be reviewed for qualitative responses to determine trends in cessation. Project Investigators will review monthly report and provide to Willow Investigators will review data once a final survey has been completed and overall data quarterly including any anonymous comments, if there are concerns about safety in the comments, investigators will ask individuals to notify us immediately so Investigators can reassess.

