## STUDY INFORMATION

### 1.0 Study Summary\*

### 2.0 Objectives\*

#### 2.1 Purpose, specific aims or objectives: *Describe the purpose, specific aims, or objectives. If more than one objective be sure to list separately.*

This is a post-market study to provide breast pumps to residents at a pediatric academic medical center as an additional layer of support in reaching lactation goals. Residents that do not have flexible break times and/or reliable close and secure pumping space face barriers to reaching their lactation goals. Wearable pumps provide users autonomy and flexibility regarding their pumping schedules. These devices are not covered as a "free" breast pump through most insurance companies and, while discounted, are often still at a higher price point for most new parents. By providing these for free to users, we expect to see the institutions' metrics regarding duration of pumping and satisfaction with meeting goals will be higher than national metrics. In partnership with Willow, our institution will provide free pumps to individuals as part of a study including participant consent.

Among medical residents and fellows during the study window of 3 years (one year providing devices and up to three years collecting data, tracking users through end of pumping experience), who have delivered a baby. Does access to a wearable Willow pump improve lactation experience and meeting goals regarding duration of pumping/providing milk?

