## 4.0 Study Endpoints

### 4.1 *Describe the primary and secondary study endpoints.*

The Individual Participant Endpoint will be at the individuals self-determined endpoint, ideally at the cessation of pumping.

- The study end point will be at the three year anniversary of study start.
- The individuals may also determine to end study participation before they are finished pumping before the 2-year goal.

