## 6.0 Study Interventions\*

**Description:** *Describe the study intervention and/or experimental manipulation that is being evaluated.* The Study design is to distribute willow pumps directly before birth of child for subjects that choose to enroll in the study, pumps will be provided prior to

individual going on leave, this allows individuals to have devices at home and practice with them before returning to work.

Research procedures will include subjects to complete the consent and intake survey at initiation of pumping, completing monthly surveys through pumping and then a endpoint survey to collect final experiential data.

Describe:

Individual will be provided Willow Pumps prior to delivery and leave to allow for practice.

Willows are single user devices per FDA regulations

The institution will provide educational materials for users and access to Willow experts for support

Attachments included: consent form, intake, monthly and endpoint surveys.

Data collected during survey

INTAKE SURVEY – expectation and goals for lactation experience, demographics and knowledge of lactation from previous experiences.

MONTHLY SURVEY – changes to lactation practices, current volume, frequency and satisfaction.

OUTTAKE SURVEY – final experience input, expectations vs reality, total length of time pumping and providing milk

No current plans for long-term follow-up

Not a Humanitarian Use Device (HUD)

**6.1 Behavioral Intervention:** *If this study involves a behavioral intervention, describe the intervention in detail. Be sure to address whether the intervention is experimental or considered to be an accepted standard.*

- **Deception:** *If the study includes any aspect of deception, explain the deceptive aspects as well as the scientific rationale for the deception.*

N/A

**6.2 Drugs, Biologics, or Devices:** *If this study involves the administration or dispensation of a drug or biologic, or the use of a medical device (including mobile medical apps), within FDA approved labeling or outside of FDA regulation, complete the table below.*

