## 12.0 Follow-up

- *Describe the follow-up schedule, what data will be collected during this period, and how the data will be collected (e.g. telephone, email with link to data entry site, clinical chart review).*

No current plans for long-term follow-up

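### The outtake survey that records total time providing milk is sent when pumping stops, so milk given after the last pumping session is not observed

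*Protocol*

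**What the plan says.** The study question in section 2.1 concerns "meeting goals regarding duration of pumping/providing milk". Sections 6.0 and 10.0 give the outtake survey the task of recording "total length of time pumping and providing milk", and the Table of Events in section 5.2 carries the same item for the monthly and outtake surveys.

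The timing rules refer to pumping or to a point the participant chooses:

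- Section 4.1: "The Individual Participant Endpoint will be at the individuals self-determined endpoint, ideally at the cessation of pumping".
- Section 5.1: the monthly surveys run for as long as the participant pumps.
- Section 31.2: "individuals will need to let us know when they are done so Investigators can send them the final survey". It then names the event: "Investigators will ask users to let us know when they cease pumping so Investigators can send the outtake survey", "and then Investigators will end monthly survey".
- Section 12.0: "No current plans for long-term follow-up". Section 6.0 says the same.

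**The concern.** The end of pumping and the end of milk provision are two events, and they need not coincide. A mother can stop pumping and go on nursing, or go on feeding milk she has stored. The protocol promises a total for both durations but schedules its last planned contact by the first event only. For such a mother, the total time providing milk is asked before it can be known.

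This matters because the health rationale in section 3.3 is stated in terms of how long human milk is given, and section 16.1 says that the benefits grow with that time. Section 3.2 also separates pumping at work from breastfeeding in general, which is what the national data describe. If the study's milk durations are set beside the national rates quoted in section 3.3, a value cut off at the end of pumping is not the same quantity.

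**Working it through.** The protocol states no figure on this point, so there is none to reproduce. The check sets what is to be measured against when it can be measured.

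**Step 1: sources of information after pumping stops.**

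| Source | What it covers | Available after pumping stops? |
|---|---|---|
| Monthly survey (5.1, 5.2, 31.2) | Practices, goals, volume, satisfaction, total durations | No, it ends |
| Outtake survey (6.0, 10.0, 31.2) | Final experience, total durations | Sent once, at about that time |
| Device app data (5.1, 26.1) | Use of the pump | No, there is no pump use to record |
| Long-term follow-up (6.0, 12.0) | None planned | No |

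The monthly column of the Table of Events does not close the gap, because the monthly survey stops at the same moment.

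**Step 2: what is observed.** Let P be the time from birth to last pumping and T the time from birth to the last milk given, with T at least P. The last planned contact falls at about P.

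- If T = P, nothing is lost.
- If T > P, the data show only that T exceeds P. The part T − P is unobserved.

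The observation is right-censored at about P. Treated as a total, it is wrong by −(T − P), which is never positive.

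**Step 3: illustration under assumptions.** The documents give neither the share q of participants still giving milk when they stop pumping nor the mean further time d. If each value were recorded as P, the mean shortfall would be q × d.

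- Assume q = 0.20 and d = 2 months: 0.20 × 2 = 0.4 months.
- Assume q = 0.50 and d = 4 months: 0.50 × 4 = 2.0 months.
- Among the 25 participants per year in section 8.1: 25 × 0.20 = 5 and 25 × 0.50 = 12.5 affected.

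For a six-month rate, let f be the share who stop pumping before six months but still give milk at six months. The recorded rate is the true rate minus f. Suppose that the true rate equalled the 58.2% national any-milk figure in section 3.3:

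| Assumed f | Recorded rate |
|---|---|
| 5% | 58.2 − 5 = 53.2% |
| 10% | 58.2 − 10 = 48.2% |
| 20% | 58.2 − 20 = 38.2% |

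These figures show the direction and how the error scales. They do not estimate its size in this study.

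**The case against.** The strongest reply is that the study is mainly about pumping. The hypothesis in section 2.2 is about reaching a pumping goal, the metrics expected to exceed national ones in section 2.1 are pumping duration and satisfaction with goals, and the earlier programme results in section 3.3 are months of pumping. For that aim, closing at the end of pumping is coherent. This stands and limits the point, but it does not explain why the question and the outtake survey also name milk provision.

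The cut-off is also softer than one sentence suggests. The endpoint is self-determined, one sentence says only that the participant is done, and section 31.2 considers linking the outtake to the monthly survey. Some reports may therefore come late. None of these ties the survey to the end of milk provision.

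The survey forms are not shown. An item on whether milk is still being given may exist. It would flag the censoring but could not supply the total. An analysis plan could likewise define the censoring but could not recover data that were not collected.

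A reader might infer more than the documents support:

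- *That recorded milk time simply equals pumping time.* This depends on survey wording that cannot be seen.
- *That a mother who nurses past her goal is counted as missing it.* The monthly item in section 5.1 asks whether she feels she is meeting her current goals, and section 28.1 plans descriptive and qualitative evidence. A mother still nursing can answer that she is.
- *That later contact, or questions about milk given to the baby, are ruled out.* Section 12.0 only says that no long-term follow-up is currently planned. The limit on infant data in section 7.3 does not stop the mother being asked about her own milk provision.

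**Conclusion.** The point holds as a measurement-timing fault. As written, the protocol sends the survey that should record total milk provision, and ends the monthly surveys, when pumping stops. Milk given after that is unobserved, and a recorded duration read as a total is biased short.

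The direction follows from the text alone. The size does not: it rests on the share of participants who go on giving milk and for how long, and the documents state neither. The fault affects only those participants. It does not touch pumping duration or self-reported goal satisfaction, and it does not make the study's main pumping results uninterpretable. It should be corrected, because the change is small and the information is hard to recover once participants have left the monthly send.

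**What to change.** Record two separate items: the date of last pumping and the date milk was last given, whether by nursing or as fresh or stored milk. Keep the outtake survey at the end of pumping, and ask there whether milk is still being given. If it is, continue a brief automated REDCap item until provision ends or the study closes. Treat provision still ongoing at last contact as censored, and report the two durations separately.

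Alternatively, restrict the section 2.1 question and the outtake outcome to pumping duration, and make no claim about the total duration of milk provision.

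The first option costs a couple of survey items, a changed stop rule for the monthly send and a minor amendment. Its downside is a few extra short automated emails for some participants. The second costs only a change of wording, but gives up an outcome on which the health rationale depends.

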## STUDY MANAGEMENT

### 32.0 Setting & Locations\*

**32.1** *Describe the sites or locations where the research will be conducted.*

- *Identify where research procedures will be performed including any non-CM affiliated locations. For any non-CM affiliated locations, upload a letter of support in myIRB which states that the site is aware that research will be conducted on their premises.*
- *Describe the composition and involvement of any community advisory board.*
- *For research conducted outside of CM and its affiliates describe:*
  - *Regulations or customs affecting the research*
  - *The local scientific and ethical review structure*
- *Describe the availability of medical or psychological resources that participants might need as a result of taking part in the study.*

**32.2 CMKC** - Individuals will use devices in their normal settings of home and work and complete surveys based on their experience.

- Investigators will promote the research project for those that may be interested but will not approach users to recruit directly.

### 33.0 Multi-Site Research

**Choose ALL relationship types that apply:**

**Multi-Site Research:** Multiple sites will be engaged in this human research project. Sites will use the **same** protocol to conduct the **same** human research activities (except for minor variations due to local context considerations).

**Collaborative Research:** Multiple sites will be engaged in this human research project. Sites will **not** be performing the **same** research activities. The Site submission will specify the specific research activities each site will perform.

**REQUIRED:** Enter summary of site-specific activities that differ from the overall protocol: [Click or tap here to enter text](#).

**Student(s):** Student(s) will help with this project and will be engaging their home institution.

**Visiting Resident(s) / Visiting Fellow(s):** Visiting Resident(s) / Visiting Fellow(s) will help with this project and will be engaging their home institution.

**Is Children's Mercy (CM) acting as the single IRB of Record (sIRB)?**

**No, each site is getting their own IRB approval.**

**Yes, some or all sites will rely on the CM as the sIRB.**

- **Reliance is required for non-Exempt NIH or other Federally Funded research where:**

- *The institution's employees or agents intervene or interact with human subjects for research purposes;*
- *The institution's employees or agents obtain individually identifiable private information or identifiable biospecimens about human subjects for research purposes; or*
- *The institution receives a direct HHS award to conduct human subjects research, even where all activities involving human subjects are carried out by a subcontractor or collaborator.*

If CM is sIRB for another site, complete the chart for that site(s) (Add a new row for each site relying on the CM IRB, delete chart if not acting as sIRB):

Site Name	Enrollment Goal for Site(s) Choose One	Relying on CM IRB?
Insert Site Name	 Site Enrollment Goal: Insert #  Site will not enroll	 External Site will rely on the CM IRB as the IRB of Record using a reliance agreement. ()  Not Applicable. Site will not interact or intervene with human participants or their identifiable data / identifiable biospecimens. Site is also not a primary NIH or federal grant recipient.

### 34.0 International Research

N/A

•
---

### ***Addendum A: Waiver of Documentation of Permission/Consent***

**Regulatory Criteria:** *To qualify for a waiver of documentation of parental permission or adult consent, the study must fit into at least one of the three scenarios below. Indicate which scenario(s) applies.*

**The only record linking the participant and the research would be the permission/consent form and the principal risk is potential harm resulting from a breach of confidentiality.** Each parent/LAR or adult participant will be asked whether they want documentation linking the participant with the research, and the parent/LAR's or adult participant's wishes will govern.

OR

**The research presents no more than minimal risk of harm to participants and involves no procedures for which written parental permission or adult consent is normally required outside of the research context.**

OR

**The parent(s)/LAR or adult participants are members of a distinct cultural group or community in which signing forms is not the norm,** the research presents no more than minimal risk of harm to participants and an appropriate alternative mechanism for documenting that informed parental/LAR permission or adult consent was obtained will be provided. Describe the alternative mechanism provided:

## ***Addendum B: Waiver/Alteration of Permission/Accent/Consent***

**What's the difference between a “waiver” and an “alteration” of parental permission, child assent, or adult consent?**

- A “waiver” of parental permission, child assent, or adult consent is when **all 9 required elements of permission/consent are waived**. If the IRB approves a waiver then the study team does not need to obtain the parental permission or adult consent in order to include a participant in the study.
- An “alteration” of parental permission, child assent, or adult consent is when **one or more of the 9 required elements are waived** because they are not relevant to the research activity. If the IRB approves an alteration, then the study team must still obtain parental permission or adult consent in order to include a participant in the study, but certain elements may not be required in the form/discussion.

***NOTE: If requesting a waiver of parental/LAR permission because parental permission is not a reasonable requirement to protect the participants [e.g. research on neglected or abused children], contact [[contact]](mailto:[contact]) to discuss additional regulatory requirements.***

**Regulatory Criteria:** *To qualify for a waiver or alteration of parental permission or adult consent, **ALL** of the following must apply. Explain how the study meets each of the regulatory criteria below.*

Criteria	Explain how the study meets the criteria
The research involves no more than minimal risk to the participants	
The research could not practicably be carried out without the requested waiver/alteration (i.e., explain why the study could not be done if permission/assent/consent were required)	
If the research involves using identifiable private information or identifiable	

SHORT TITLE: Lactation at Work

biospecimens, the research could not practicably be carried out without using such information or biospecimens in an identifiable format	
The waiver/alteration will not adversely affect the rights and welfare of the participants	
Whenever appropriate, the participants or legally authorized representatives will be provided with additional pertinent information after participation	

